### ***3.3. IntellaMap Orion High Resolution Mapping Catheter***

The IntellaMap Orion High Resolution Mapping Catheter is an 8.5F, 115 cm working length, 64-electrode steerable catheter. The basket-shaped distal region consists of eight splines that comprise the electrode array. The proximal end has a handle that extends to a cable with a connector. The handle includes bi-directional articulation controls and a deployment slider that activates the electrode array into a basket shape once inside the heart. A flushing port extends from the back of the connector for connection to a continuous pressurized saline drip. The catheter is supplied with an 8.5F insertion sleeve for insertion through the hemostasis valve of an introducer sheath. A sensor in the catheter tip enables the position of the distal region of the catheter to be tracked in space when used with the Rhythmia™ Mapping System. Subsequent versions of the IntellaMap Orion mapping catheter may be used during this study as they become commercially available after regulatory approval in their geography.

## 4. Study Objectives and Endpoints

The purpose of the INTERRUPT AF study is to obtain data for the Rhythmia™ Mapping System in conjunction with Boston Scientific Open-Irrigated (OI) Catheters for ablation of Paroxysmal Atrial Fibrillation according to current international and local guidelines.

The primary objective of the study is to assess acute and long-term outcomes for the Rhythmia Mapping System in conjunction with Boston Scientific Open-Irrigated Ablation Catheters to treat Paroxysmal Atrial Fibrillation for de novo cases. In addition, the study serves to comply with the FDA request of a PAS for the Blazer OI, IntellaNav OI, IntellaTip MiFi OI, and IntellaNav MiFi OI Ablation catheters.

### 4.1. Primary Safety Endpoint

The primary safety endpoint is defined as the safety event-free rate at 12 months post-procedure.

Primary safety events will consist of a composite of acute primary safety events, (events occurring within seven days post-procedure or hospital discharge, whichever is later), and chronic primary safety events (events occurring through 3 or 12 months post-procedure).

Acute primary safety endpoint events will be defined as the following:

- Death
- Myocardial infarction (MI)
- Vagal Nerve Injury/Gastroparesis
- Transient ischemic attack (TIA)
- Stroke/Cerebrovascular accident (CVA)
- Thromboembolism
- Pericarditis
- Cardiac tamponade/perforation
- Pneumothorax
- Vascular access complications
- Pulmonary edema/heart failure
- AV block

Chronic primary safety endpoint events will be defined as the following:

- Occurring through 3 Months post-procedure
  - Atrial esophageal fistula
  - Pericardial effusion
- Occurring through 12 Months post-procedure
  - Pulmonary vein stenosis (symptomatic and requiring intervention)

**Table 1: Primary Safety Endpoint Definitions**

Term	Definition
Atrio-Esophageal Fistula	A connection between the atrium and the lumen of the esophagus

**Table 1: Primary Safety Endpoint Definitions**

Term	Definition
AV block	A conduction disturbance that results in the partial inability of an electrical impulse generated in the atria to reach the ventricles.
Cardiac tamponade/ Perforation	The development of a significant pericardial effusion during or within 30 days of undergoing an AF ablation procedure. A significant pericardial effusion is one that results in hemodynamic compromise, requires elective or urgent pericardiocentesis, or results in a 1-cm or more pericardial effusion as documented by echocardiography. 
Myocardial infarction (in the context of AF ablation)	The presence of any one of the following criteria: (1) detection of ECG changes indicative of new ischemia (new STT wave changes or new LBBB) that persist for more than 1 hour; (2) development of new pathological Q waves on an ECG; (3) imaging evidence of new loss of viable myocardium or new regional wall motion abnormality. 
Pericardial Effusion	A collection of fluid or blood in the pericardial space around the heart or in pleural space around the lungs. 
Pericarditis	Inflammation of the pericardium surrounding the heart. Pericarditis should be considered a major complication following ablation if it results in an effusion that leads to hemodynamic compromise or requires pericardiocentesis, prolongs hospitalization by more than 48 hours, requires hospitalization, or persists for more than 30 days following the ablation procedure. 
Pneumothorax	Collapse of the lung due to an abrupt change in the intrapleural pressure within the chest cavity.
Pulmonary edema/heart failure	Ineffective pumping of the heart leading to an accumulation of fluid in the lungs. Typical symptoms include shortness of breath with exertion, difficulty breathing when lying flat and leg or ankle swelling.
Pulmonary Vein Stenosis (Significant)	Pulmonary vein stenosis is defined as a reduction of the diameter of a PV or PV branch. For the primary safety endpoint of this study, significant pulmonary vein stenosis is defined as symptomatic and requiring intervention.
Stroke/Cerebrovascular accident (CVA)	Rapid onset of a focal or global neurological deficit with at least one of the following: change in level of consciousness, hemiplegia, hemiparesis, numbness or sensory loss affecting one side of the body, dysphasia or aphasia, hemianopia, amaurosis fugax, or other neurological signs or symptoms consistent with stroke. Duration of a focal or global neurological deficit $\geq$ 24 hours; OR $<$ 24 hours if therapeutic intervention(s) were performed (e.g., thrombolytic therapy or intracranial angioplasty); OR available neuroimaging documents a new hemorrhage or infarct; OR the neurological deficit results in death. No other readily identifiable non-stroke cause for the clinical presentation (e.g., brain tumor, trauma, infection, hypoglycemia, peripheral lesion, pharmacological influences). Confirmation of the diagnosis by at least one of the following: neurology or neurosurgical specialist; neuroimaging procedure (MRI or CT scan or cerebral angiography); lumbar puncture (i.e., spinal fluid analysis diagnostic of intracranial hemorrhage) 
Thromboembolism	The blockage of a blood vessel lumen by air or solid material such as device fragments, blood clot or other tissues that have migrated from another anatomic site.

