#### 9.1.1.2. Sample Size

The sample size estimate was obtained using the normal approximation to the binomial distribution and verified through simulations based on Kaplan-Meier methodology. The following assumptions were used in the sample size calculation:

Assumptions	Primary Safety
Expected rate	90% 
Performance goal	85%
Attrition (per year)	7.5%
Significance level (one-sided)	5%
Power	80%

Under the hypothesis and assumptions outlined above, the required sample size for this endpoint is 329 TREATMENT subjects.

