## 17. Committees

### 17.1. *Safety Monitoring Process*

Clinical Sites will report all study device related AEs, study procedure related AEs, and serious AEs to the sponsor as assessed by the clinical investigator. Investigators will be tasked to determine whether a subject has experienced one of the events specified in Section 4.1, counting towards the primary safety endpoint.

Since device and procedure relatedness do not affect the study endpoints, an independent CEC is not necessary to eliminate bias. The determination of relatedness is used for BSC safety assessment, but not in determining endpoint events. NOTE: The primary safety endpoint includes all deaths within 7 days or pre-discharge (whichever is later) regardless of relatedness to study device or procedure.

All reported adverse events will be reviewed on a regular basis by BSC's Medical Safety Group and study team to evaluate subject safety. The BSC Medical Safety group includes physicians with expertise in Electrophysiology and with the necessary therapeutic and subject matter expertise to evaluate and classify the events. During scheduled monitoring activities, clinical research monitors will support this continuous review through their review of source document and other data information.

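### The AV block definition in the primary safety composite covers only partial conduction failure, so read literally it leaves out complete AV block

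*Protocol*

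**What the plan says.** Protocol Section 4.1 lists the component by name only, at the end of the acute events: "Pulmonary edema/heart failure - AV block". The Synopsis, Protocol Section 9.1.1 and SAP Section 3.1 list it in the same way, with no degree, duration or severity attached.

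The only definition is in Protocol Table 1, within Section 4.1: "A conduction disturbance that results in the partial inability of an electrical impulse generated in the atria to reach the ventricles". Table 11 in Section 23.2 repeats it. Neither table mentions complete or third-degree block, and the SAP defines no safety component.

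On who applies the definition, Protocol Section 17.1 states: "Investigators will be tasked to determine whether a subject has experienced one of the events specified in Section 4.1". It adds that "an independent CEC is not necessary to eliminate bias", because relatedness plays no part in the endpoints. The same section has the sponsor's Medical Safety Group, which includes physicians with electrophysiology expertise, review all reported adverse events and classify them.

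**The concern.** A definition limited to partial failure does not, on its plain meaning, include total failure. The listed term carries no such limit, so the list and the definition disagree about whether complete AV block is an endpoint event.

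The composite is tested pass/fail against an 85% performance goal, and both primary endpoints must pass for study success. A site that reads the term in its ordinary clinical sense would count complete block; a site that follows the table would not. The stated reason for having no independent committee concerns relatedness. It does not address whether an event meets a component definition, which is the question here. Any event dropped on the literal reading raises the observed event-free rate, so the error can only run towards passing.

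**Working it through.** **The texts side by side**

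| Place | Wording | Complete block included? |
|---|---|---|
| Protocol Synopsis, 4.1 and 9.1.1; SAP 3.1 | AV block, unqualified | Yes, on the ordinary sense of the term |
| Protocol Tables 1 and 11 | partial inability to conduct | No, read literally |
| SAP | no definition | Does not resolve it |

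No other text in either document settles the matter.

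**Inputs for the size of the effect** (Protocol 9.1.1.2 and 9.1.1.3): performance goal 85%, expected rate 90%, attrition 7.5% per year, one-sided level 5%, power 80%. The endpoint passes if the one-sided 95% log-log lower limit exceeds 85%.

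**The plan's sample size.** The plain normal approximation gives n = [(1.645·√(0.85·0.15) + 0.842·√(0.90·0.10)) / 0.05]² = 282.1, so 283, and 283/0.925 gives 306. With a continuity correction, n = 302 and 302/0.925 gives 327. The exact binomial, taking the smallest n from which power stays at or above 80%, gives 304, and 304/0.925 = 328.6, so 329. The stated 329 is reproduced. None of its inputs depends on the AV block wording, so correcting the definition leaves it unchanged.

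**Pass boundary at N = 329.** Assume complete follow-up, or equivalently that all events are acute and precede any censoring. With e events, S = 1 − e/N, se = √[e/(N(N−e))] / |ln S|, and the lower limit is S^exp(1.645·se).

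- e = 38: S = 291/329 = 88.45%, se = 0.1623, lower limit 85.19%: pass.
- e = 39: S = 290/329 = 88.15%, se = 0.1602, lower limit 84.85%: fail.

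Each omitted event raises the observed rate by 1/329 = 0.30 percentage points.

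**Chance of passing if a share m of subjects has a true event that goes uncounted.** With true event-free rate q, this is P[Binomial(329, 1 − q − m) ≤ 38]. The documents give no value for m, so the range below is assumed. It treats every such subject as omitted and as having no other endpoint event.

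| m (assumed) | Subjects of 329 | q = 85% | q = 90% |
|---|---|---|---|
| 0 | 0 | 4.3% | 84.8% |
| 0.1% | 0.3 | 4.8% | 86.2% |
| 0.25% | 0.8 | 5.6% | 88.2% |
| 0.5% | 1.6 | 7.2% | 91.0% |
| 1.0% | 3.3 | 11.3% | 95.2% |

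**A single omitted event** reverses the result only if the true count is exactly 39. That has probability 3.7% when q = 90% and 1.7% when q = 85%, and it further requires that a complete block occurs and is excluded.

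**The case against.** The strongest reply is that nobody will apply the definition literally. Every listing says AV block without qualification, the investigators perform ablation for a living, and an electrophysiologist would have to decide that complete AV block is not AV block. Several other Table 1 entries, such as pneumothorax and pulmonary edema/heart failure, are also descriptive glosses. This reply largely stands on likelihood: most investigators would probably count complete block. It does not remove the conflict between list and definition, and it supports correcting the definition to match the evident intent.

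A reader might infer that nobody reviews the investigators' calls. Section 17.1 does not support that. Sponsor physicians review and classify reported events, and monitors support this through source review. That review is not independent, however, the documents do not say that it can overrule an investigator's endpoint decision, and they supply no other definition for it to use.

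A reader might also infer that such events would disappear from view. They would not. Protocol Section 15.1 requires all serious, procedure-related and device-related adverse events to be reported, and Section 9.1.4 has their rates tabulated. The possible loss is from the composite only.

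Finally, the boundary of 38 events holds only for 329 subjects with complete follow-up. Section 9.2.1 uses all eligible subjects, so the actual boundary will differ. That one event can decide a result at the boundary is also true of any component of any composite.

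**Conclusion.** The definition is wrong as written: applied literally, it excludes complete AV block from a pass/fail safety composite whose listed term would include it. The consequence is possible omission or inconsistent counting, with any bias towards passing.

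The stronger reading, that the composite will count mild block and miss the most serious form, is not supported. The documents do not rank degrees of block, show no intent to exclude complete block, and give no evidence that sites would exclude it.

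The size is probably small. If 0.1% to 0.5% of subjects went uncounted and the true event-free rate were 85%, the chance of passing would be 4.8% to 7.2% instead of 4.3%. This rests on an assumed omission rate, on 329 subjects with complete follow-up, and on every such event being left out, which is unlikely. No figure in the plan is in error because of this point. It is a minor correction that is worth making.

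**What to change.** In Protocol Tables 1 and 11, change *partial inability* to *partial or complete inability*. Have SAP Section 3.1 refer to that definition. Make both changes before endpoint classification is finalised, so that all sites and the sponsor's reviewers apply one rule.

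The cost is two added words in each table and a cross-reference in the SAP. It goes through a protocol amendment, which under Section 12.3 needs ethics review before it takes effect, so it is best bundled with the next one. Sample size, visits and procedures are unaffected. Any AV block events already classified should be checked against the corrected wording.

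This edit settles only whether complete block counts. It does not say whether brief or lower-degree block should count; if the sponsor wants a degree or duration threshold, that needs a separate statement in the same tables.

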**Table 11: Definitions**

Term	Definition
Cardiac tamponade/ perforation	The development of a significant pericardial effusion during or within 30 days of undergoing an AF ablation procedure. A significant pericardial effusion is one that results in hemodynamic compromise, requires elective or urgent pericardiocentesis, or results in a 1-cm or more pericardial effusion as documented by echocardiography.
Embolism	The sudden blocking of an artery by a clot or foreign material which has been brought to its site of lodgment by the blood current.
Enrolled Subject	A subject who is eligible for enrollment and signs an informed consent document to participate in the study.
Hematoma	A localized collection of blood, usually clotted, in an organ, space or tissue, due to a break in the wall of a blood vessel.
INTENT Subject	Any subject that signs the consent form but does not have any study devices inserted into the body. Subjects who are enrolled in the study but do not undergo ablation procedure within 60 days from consent signature date may not be reconsented and will be withdrawn from the study.
In-patient Hospitalization	Hospitalizations $\geq 24$ hours in duration or $<24$ hours with medical intravenous therapy or surgical intervention
Myocardial infarction (in the context of AF ablation)	The presence of any one of the following criteria: (1) detection of ECG changes indicative of new ischemia (new STT wave changes or new LBBB) that persist for more than 1 hour; (2) development of new pathological Q waves on an ECG; (3) imaging evidence of new loss of viable myocardium or new regional wall motion abnormality
Paroxysmal Atrial Fibrillation (PAF)	Recurrent symptomatic Atrial Fibrillation that terminates spontaneously or with intervention within seven days of onset.
Pericardial Effusion	A collection of fluid or blood in the pericardial space around the heart or in pleural space around the lungs.
Pericarditis	Inflammation of the pericardium surrounding the heart. Pericarditis should be considered a major complication following ablation if it results in an effusion that leads to hemodynamic compromise or requires pericardiocentesis, prolongs hospitalization by more than 48 hours, requires hospitalization, or persists for more than 30 days following the ablation procedure.
Pneumothorax	Collapse of the lung due to an abrupt change in the intrapleural pressure within the chest cavity.

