3.1 Primary Safety Endpoint

Safety will be evaluated by the primary safety event free rate at 12 months post procedure. Primary safety events will consist of a composite of acute primary safety events (events occurring within seven days post-procedure or hospital discharge, whichever is later), and chronic primary safety events (events occurring through 3 or 12 months post-procedure).

Acute primary safety events will be defined as the following:

- Death
- Myocardial infarction (MI)
- Vagal Nerve Injury/Gastroparesis
- Transient ischemic attack (TIA)
- Stroke/Cerebrovascular accident (CVA)
- Thromboembolism
- Pericarditis
- Cardiac tamponade/perforation
- Pneumothorax
- Vascular access complications
- Pulmonary edema/heart failure
- AV block

Chronic primary safety events will be defined as the following:

- Occurring through 3 Months post-procedure
 - Atrial esophageal fistula

- Pericardial effusion
- Occurring through 12 Months post-procedure
- Pulmonary vein stenosis (symptomatic and requiring intervention)

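### The primary safety event called pericardial effusion is defined to include pleural fluid, so any reportable pleural effusion through 3 months meets it

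*Protocol*

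**What the plan says.** Protocol Table 1, which sits in Section 4.1 and defines the primary safety terms, extends pericardial effusion to fluid or blood "or in pleural space around the lungs". Table 11 has the same definition: "A collection of fluid or blood in the pericardial space around the heart or in pleural space around the lungs".

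Protocol 4.1 and 9.1.1 list the component among the chronic events, under "Occurring through 3 Months post-procedure". SAP 3.1 lists "Pericardial effusion" in the same 3-month group and does not define it.

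Other components in Table 1 are limited. For pulmonary vein stenosis: "For the primary safety endpoint of this study, significant pulmonary vein stenosis is defined as symptomatic and requiring intervention". Tamponade/perforation concerns the pericardium only and has criteria: "A significant pericardial effusion is one that results in hemodynamic compromise, requires elective or urgent pericardiocentesis", or an echocardiographic size of at least 1 cm.

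Protocol 17.1 leaves it to the investigator to decide whether an event in Section 4.1 has occurred, and states: "Since device and procedure relatedness do not affect the study endpoints, an independent CEC is not necessary to eliminate bias".

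Protocol 15.1 limits what sites report to serious adverse events, device- or procedure-related adverse events, device deficiencies and unanticipated device effects.

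**The concern.** Fluid in the pleural space is not a pericardial effusion, yet the endpoint definition makes it one. The definition sets no limit on size, symptoms, treatment or cause, and relatedness does not filter endpoint events. A serious pleural effusion from pneumonia at week 10, for example, is reportable and meets the definition.

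Two things are at stake. The first is consistent classification. The study plans 25 to 50 centers (Protocol 5.1) and has no independent committee. One investigator may read the term by its name and not count pleural fluid, while another applies Table 1 and counts it. The second is the safety test itself. Pleural events lower the event-free rate compared with 85%, and both primary endpoints must pass for study success (Protocol 9.1, 9.2.3). The same event definition also feeds the Kaplan-Meier safety analyses in the FDA progress reports (Protocol 9.3.1).

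**Working it through.** **Definition, place by place**

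| Question | Where | Answer |
|---|---|---|
| Does the definition cover pleural fluid? | Protocol Tables 1 and 11 | Yes, same wording in both |
| Does it count toward the primary endpoint? | Protocol 4.1, 9.1.1; SAP 3.1 | Yes, through 3 months |
| Is there a size, severity or cause limit? | Table 1 | No |
| Is there a relatedness filter on the endpoint? | Protocol 17.1 | No |
| Does the SAP narrow it? | SAP 3.1 | No |
| Which effusions reach the sponsor? | Protocol 15.1 | Serious, or device- or procedure-related |
| Is imaging routine? | Protocol Table 5, 8.6, 8.8 | No; only if pulmonary vein stenosis is suspected or per center practice |

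The definition therefore covers every pleural collection, while the reporting rules decide which ones can be counted.

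**Reproducing the plan's 329**

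Inputs (Protocol 9.1.1.2): goal 85%, expected rate 90%, one-sided 5%, power 80%, attrition 7.5%. The smallest n from which exact binomial power stays at or above 80% is 304. Dividing by (1 − 0.075) gives 304/0.925 = 328.6, so 329. The normal approximation with continuity correction gives 302, or 327 after attrition, which is close. The planned number reproduces and this point does not change it.

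**Events allowed under the planned rule**

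With n subjects, d events and no censoring, S = 1 − d/n, and the one-sided 95% log-log lower limit is

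L = S^exp(1.645 × √[d/(n(n − d))] / |ln S|).

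At n = 329:
- d = 38: S = 0.8845, √[38/(329 × 291)] = 0.01992, |ln S| = 0.12273, exponent exp(1.645 × 0.1623) = 1.306, L = 0.852. Pass.
- d = 39: S = 0.8815, L = 0.849. Fail.

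So at most 38 events are allowed. The planned 10% event rate implies 32.9 expected events.

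**Illustration of sensitivity**

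Let x be the share of otherwise event-free subjects who have pleural fluid only. This is an assumption; the documents give no rate. If the 90% planning rate excludes such events, the true event-free rate becomes 0.90 × (1 − x), and power is the binomial probability of 38 or fewer events in 329 (35 or fewer in 304, the number left after 7.5% attrition).

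| x | True rate | Expected events, n = 329 | Power, n = 329 | Power, n = 304 |
|---|---|---|---|---|
| 0 | 90.0% | 32.9 | 84.8% | 84% |
| 0.5% | 89.55% | 34.4 | 77.4% | 76% |
| 1% | 89.1% | 35.9 | 68.6% | 68% |
| 2% | 88.2% | 38.8 | 48.7% | 48% |

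As a cross-check, Kaplan-Meier simulation of the log-log rule at 329 with 7.5% attrition gave about 85% at the planned rate. With 0.5, 1 and 2 percentage points of added events it gave 77%, 65% and 44%. The last two are lower partly because whole points are added: 2% of the 90% event-free is 1.8 points.

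**The case against.** A reader might infer that every pleural effusion in the first 3 months will be counted. The documents do not support that. A non-serious effusion judged unrelated to device or procedure is not reportable under Protocol 15.1, and without routine imaging many small silent collections would go unseen. This objection stands and narrows the claim to reported effusions. It does not change the definition, and it leaves capture dependent on center practice.

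A reader might also infer that the study has lost power. That is not shown either. Both documents attribute the 90% rate to the ZERO-AF data and the 85% goal to two other studies, without saying which effusion definition those sources used. If the 90% already contains pleural events, planned power does not fall. In addition, 329 is a minimum from 415 enrolled (Protocol 5.1, 9.1.5), and Protocol 9.2.1 uses all eligible subjects, so the number analyzed may be larger.

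The direction is conservative. Added events make the goal harder to meet and cannot create a false safety pass; the risk falls on the sponsor's chance of success.

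The wording may also have been adopted on purpose: Table 1 attaches a literature reference to it and Table 11 repeats it. Deleting it unchecked would loosen a primary safety endpoint in an FDA-mandated study and could break comparability with the benchmarks. This stands as a reason to check before deleting.

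Finally, the missing severity threshold is not peculiar to pleural fluid. AV block and pneumothorax have none, nor does pericardial fluid under this component. The point here is therefore the anatomical mismatch between term and definition.

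**Conclusion.** The point holds as a defect in a primary endpoint definition. As written, a reported pleural effusion through 3 months is a primary safety event regardless of cause or size, and nothing in the SAP or the safety review process resolves the conflict between the term and its definition. The certain consequence is that two reasonable investigators can classify the same event differently.

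The effect on power is possible but unproven. The fall from about 85% to 77%, 69% or 49% rests on assumed pleural-only rates of 0.5%, 1% and 2%, on a 90% planning rate that excludes pleural events, and on exactly 329 analyzed subjects. The figures do show how little room there is: about 33 events are expected and 38 are allowed. The correction is cheap and should be made.

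**What to change.** 1. Check whether the sources of the 90% expected rate and the 85% goal counted pleural collections as pericardial effusion.
2. If they did not, delete "or in pleural space around the lungs" from Protocol Tables 1 and 11.
3. If pleural collections were meant to count, list them as a separately named component of the primary safety endpoint.
4. Handle other pleural effusions under the existing reporting rules of Protocol 15.1. Non-serious, unrelated ones would remain unreported, as now.
5. Have SAP 3.1 cite the agreed definition, fixed before the endpoint analysis.

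The cost is a check of the benchmark definitions, one phrase in two tables and a cross-reference in the SAP. The sample size does not change.
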